2.2 Time schedule

The time schedule of this trial is detailed in table 1.

Table 1: Time schedule of the trial (Part A and Part B)

First patient first visit (FPFV):	November 2021
Last patient first visit (LPFV):	September 2022
Last patient last visit (LPLV):	September 2023
Analysis	October 2022 (Primary endpoint analysis)
End of study definition	The end of study will be on the day of database lock.
End of trial	November 2023
Final study report:	December 2023

End of study will be on the day of database lock, as planned 30 days after the last patient last visit.

3 Discussion of trial design

According to section 4.2 of the accompanying master protocol:

Trials under the master protocol allow testing of different booster strategies to assess their immunogenicity and safety against SARS-CoV-2 and its variants. Different trial populations, different vaccines, additional doses and vaccination time points, and extended follow-up visits can be added throughout amendments of the master protocol or trials under the master protocol.

Specific to this trial:

This trial is a sub-protocol embedded within the master protocol EU-COVAT: A Randomised, Controlled, Adaptive, Multicentre, Phase II Master Protocol Evaluating Different Booster Strategies in Individuals Already Vaccinated Against SARS-CoV-2.

This is a randomised controlled, adaptive, evaluator-blinded multicentre Phase II protocol evaluating immunogenicity and reactogenicity of different booster strategies in individuals 75 years and older after a primary vaccination series against SARS-CoV-2. This trial foresees testing of different vaccines as a 3rd (Part A) or 4th (Part B) vaccination dose (refer to section 4.2 in the current protocol) for comparative assessment of their immunogenicity and safety against SARS-CoV-2 wild-type and

variants in the elderly, a usually neglected population. Different vaccines and extended follow-up visits can be added by means of amendments to this trial. As stated in the master protocol, this trial implements a specific safety monitoring strategy for a control group as implemented in the EU-COVAT subprotocol with the EudraCT no.: 2021-004889-35, a separate sub-protocol embedded within the EU-COVAT master protocol (see below). This control group is used for exploratory comparison.

Vaccines used in this trial will be those already marketed and in their commercial presentation. In part B the sample size planned is adequate for a precise enough estimation of the immune response after a 4th vaccination dose.

4 Selection of trial population

According to section 4.4 of the accompanying master protocol:

VACCELERATE has established a European volunteer registry for vaccine trials. A continuously growing number of interested individuals have expressed their interest in this registry. This will allow for fast and efficient recruitment of trial participants.

Subjects to be recruited in the trials under the master protocol will be those already fully vaccinated (all-comers) with no contra-indication against any of the vaccine products in the trial at the moment of inclusion and as specified in respective sub-protocol.

Within each trial, subjects will be stratified (as applicable and specified per sub-protocol) by:

- Gender (female/male).
- Vaccine product used for primary vaccination (BNT162b2; mRNA-1273; ChAdOx-1-S; other)
- Immune status (competent, immunocompromised).

Documented history of prior COVID-19 infection.

Reasons for gender distribution

Subjects included in this trial are expected to be similar to subjects that have been vaccinated within the vaccination programs in each country. Therefore, gender distribution in the present trial is expected to be similar to that of the general vaccinated population and no restrictions will be made with relation to biological sex, unless included in the selection criteria.

Specific to this trial, Part B:

EU-COVAT-1_AGED_SAP_V03_0

Subjects included in this trial are expected to be similar to subjects that have been vaccinated within the vaccination programs in each country. Gender distribution will be therefore similar to that of the population vaccinated so far. Accordingly, Part B will include 550 subjects that are randomised 1:1 to either BNT162b2 or mRNA-1273. Recruitment of cohorts will be closed when the pre-planned number for each cohort is reached. Stratification is planned according to the pre-study vaccination series eligible for Part B (primary vaccination plus 3rd vaccine dose (= first booster), gender (female/male), documented history of prior COVID-19 infection (yes/no), as applicable and defined also by enrolment criteria.

Inclusion criteria

- Subject is ≥75 years old.
- For study entry in **Part B** the subject was vaccinated with one of the following vaccination regimens (1st + 2nd + 3rd dose):
 - BNT162b2 + BNT162b2 + BNT162b2
 - BNT162b2 + BNT162b2 + mRNA-1273
 - mRNA-1273 + mRNA-1273 + mRNA-1273
 - mRNA-1273 + mRNA-1273 + BNT162b2
 - ChAdOx-1-S + ChAdOx-1-S + BNT162b2
 - ChAdOx-1-S + ChAdOx-1-S + mRNA-1273
- The last dose of the above vaccinations must have been administered at least 1 month prior to study entry. Vaccination status should be documented in the source data and will be captured in the eCRF.
- No contra-indication against any of the vaccine products in the trial.
- Written informed consent from subject has been obtained.

Exclusion criteria

- Prior to study entry the subject got vaccinated with a regimen not included in the above list.
- Last anti-SARS-CoV-2 vaccine dose administered less than one month prior to study entry.
- Vaccination against a disease other than COVID-19 within 2 weeks prior to study entry. Only exception: Influenza vaccination which is allowed at any time.
- Subjects with any significant or uncontrolled disease posing a risk due to vaccination as judged by the investigator.

- Current immunosuppressive therapy, for example continuous glucocorticosteroid treatment equivalent to >10 mg/day prednisolone.
- Subject simultaneously participates in another clinical trials or has participated in the past 30 days.
- Subjects unable to report solicited adverse events.
- Subject participates or participated in Part A of this trial.
- Subject with any contraindications to the vaccines in the trial. A list of contraindications as listed in the Summary of medicinal Product Characteristics (SmPC, the Fachinformation in Germany), if appropriate.
- Use of drugs with significant interaction with the investigational product according to the SmPC or similar documents.
- Diseases or findings that may have a significant effect on the target variables and which may therefore mask or inhibit the therapeutic effect under investigation.
- Subject had COVID-19 or tested positive for SARS-CoV-2 within the last 3 months.
- Persons with any kind of dependency on the principal investigator or employed by the sponsor or principal investigator.
- Legally incapacitated persons.
- Persons held in an institution by legal or official order.

Withdrawal of trial subjects after trial start

According to section 4.5. of the accompanying master protocol:

A participant may withdraw from the study at any time at his/her own request or may be withdrawn at any time at the discretion of the investigator for safety, behavioural, or compliance/adherence reasons. This is expected to be uncommon. When a participant withdraws before study completion, the reason for withdrawal is to be documented in the eCRF and in the source document. If the reason for withdrawal from the study is withdrawal of consent, then no additional assessments are allowed. The participant will be permanently discontinued from the study intervention and the study at that time. If the participant withdraws consent for disclosure of future information, the sponsor may retain and continue to use any data collected before such a withdrawal of consent. If a participant withdraws from the study, he/she may request destruction of any samples taken and not tested, and the investigator must document this in the study site records.

5 Treatments to be given

According to section 4.7.1. of the accompanying master protocol:

Vaccines to be evaluated in sub-protocols under the master protocol will be vaccines with marketing authorization at the time of each sub-protocol design and/or vaccines still in clinical development, i.e., pre-authorisation. Vaccines to be administered in the intervention and control arms will be defined in each sub-protocol depending on the hypothesis and the booster strategies tested.

Subjects allocated to control arms could receive a 3rd vaccine dose or not receive a 3rd vaccine dose.

Specific to this trial, Part B:

Study vaccines will be given as a 4th dose in subjects already vaccinated with defined prior vaccination strategies (with BNT162b2, mRNA-1271 or ChAdOx-1-S) as per eligibility criteria. The vaccines to be evaluated as 4th vaccination (second booster) dose will be BNT162b2 (Comirnaty®) and mRNA-1273 (Spikevax®). For a detailed overview of all cohorts and arms in this study please refer to Tables 2.1 and 2.2 below.

In Part B there is a minimum interval of 1 month between the on-study 4th vaccination dose and the 3rd pre-study vaccination, with longer intervals as per local regulation or practice.

Table 2.2: Intervention in Part B - 4th vaccination dose

Cohort	Vaccination prior to study entry	Arm	Study intervention: 4 th vaccination dose*
Cohort 4	BNT162b2 +	7	BNT162b2
	BNT162b2 + BNT162b2	8	mRNA-1273
Cohort 5	BNT162b2 +	9	BNT162b2
	BNT162b2 + mRNA-1273	10	mRNA-1273
Cohort 6	mRNA-1273 +	11	BNT162b2
	mRNA-1273 + mRNA-1273	12	mRNA-1273
Cohort 7	mRNA-1273 +	13	BNT162b2
	mRNA-1273 + BNT162b2	14	mRNA-1273
Cohort 8	ChAdOx-1-S +	15	BNT162b2
	ChAdOx-1-S + BNT162b2	16	mRNA-1273
Cohort 9	ChAdOx-1-S +	17	BNT162b2
	ChAdOx-1-S + mRNA-1273	18	mRNA-1273

* administered at least 1 month after the 3rd pre-study vaccination.

6 Assignment of trial subjects to treatment groups

According to section 4.7.5 of the accompanying master protocol:

Subject fulfilling selection criteria will be randomised to the different treatment arms in the trial through a central procedure. Randomisation will be stratified according to:

- Vaccine product used for primary vaccination (detailed in the concerned sub-protocol).
- Trial Site.
- Gender (female/male).
- Immune status (competent, immunocompromised as applicable in the concerned sub-protocol).
- Documented history of prior COVID-19 infection (none, asymptomatic, symptomatic/pre-vaccination or post-vaccination).

The participants are randomised into the study arms as defined in each sub-protocol. Randomisation will be implemented by a 24/7-Internet service (ALEA 17.1, FormsVision BV, Abcoude, NL) and prepared centrally by the Institute of Medical Statistics and Computational Biology (IMSB) at the University of Cologne.

Specific to this trial, Part B:

Subjects fulfilling selection criteria will be randomised to 4th dose through a central procedure.

Subjects will be randomised in a 1:1 ratio to one of the two treatment groups:

- 4th vaccination with BTN162b2 (Comirnaty®), including modified vaccine product.
- 4th vaccination with mRNA-1273 (Spikevax®), including modified vaccine product.

Randomisation will be stratified as described below:

Stratification is planned according to the pre-study vaccination series eligible for Part B (primary vaccination plus 3rd vaccine dose (= first booster), gender (female/male), documented history of prior COVID-19 infection (yes/no), as applicable and defined also by enrolment criteria.

In this trial, there is no stratification in the randomisation

- according to the status of immune competency of the trial subject.
- according to trial site.

7 Efficacy and safety endpoints

According to section 4.8 of the accompanying master protocol:

Main overarching immunogenicity variables to be included in the sub-protocols are those standard tests showing the immune response to SARS-CoV-2 vaccines, as described below.

Overarching safety variables of interest include unsolicited and solicited adverse events day 14, as applicable, after a 4th vaccination dose administration and severe adverse events for the duration of the trial.

Specific to Part B of this clinical trial:

This trial aims to evaluate immunogenicity and safety of a 4th vaccination dose of COVID-19 vaccines in older (≥ 75) subjects having received a primary vaccination series plus a 3rd vaccine dose > 1 month ago at the time of enrolment.

Primary endpoints

According to section 4.8.1.1 of the accompanying master protocol:

- Rate of 2-fold antibody titre increase 14 days **after the 4th vaccination dose** measured by quantitative enzyme-linked immunosorbent assay (Anti-RBD-ELISA) against wild-type virus.

Safety endpoints

- Unsolicited AEs until the end of trial.
- Solicited AEs for 7 days after a 4th vaccination dose.
- Rate of severe adverse events (AEs) Grade ≥ 3 according to the National Cancer Institute Common Toxicity Criteria up to three months after a 4th vaccination dose (Note: Adverse events Grade ≥ 3 must be reported as SAE by using study specific SAE reporting process, see section 7.3).

Secondary endpoints

- Change in neutralizing antibody titre (Virus Neutralisation Assay) **against wild-type** 14 days after a 4th vaccination dose, to be determined in a subgroup only.

- Change in neutralizing antibody titre (Virus Neutralisation Assay) **against variants of concern** 14 days after a 4th vaccination dose, to be determined in a subgroup only.
- Antibody titre level **12 months** after a 4th vaccination dose measured by a quantitative enzyme-linked immunosorbent assay (anti-RBD-ELISA assay).
- Neutralizing antibody titre (Virus Neutralisation Assay) **against wild-type SARS-CoV-2** at 12 months after a 4th vaccination dose, to be determined in a subgroup only.
- Neutralizing antibody titre (Virus Neutralisation Assay) **against variants of concern** at 12 months after a 4th vaccination dose, to be determined in a subgroup only.

Exploratory endpoints

- Change in cellular immune response measured by qPCR 14 days after 4th booster dose, to be determined in a subgroup only.
- Neutralising capacity measured by neutralising activity against newly emerging variants in bio-banked samples in a subgroup analysis after a 4th vaccination dose, to be determined in a subgroup only.

d: for secondary use defined in informed consent; also optional at visit 1 and visit 2: at trial site and upon agreement of trial participant additional blood collection for biobanking of peripheral blood mononuclear cells (PBMC) as per informed consent

e: solicited AEs are recorded by trial participant till Day 7 and records will be collected at visit 2 (Day 14) by trial staff and captured in eCRF; unsolicited AEs are recorded by trial investigator until the end of trial as described in this protocol.

f: medical history includes information on prior SARS-CoV-2 infection and COVID-19 disease if applicable; name of SARS-CoV-2 variant should be documented if known.

[§]Administration of 4th vaccination dose after blood sampling for immunogenicity and cellular immunity during visit 1. Trial participant is observed for any adverse reaction for at least 15 min or according to standard of care upon vaccination.

Note: The protocol does not foresee withdrawal of subjects with SARS-CoV-2 after randomization (by means of anti-Nucleocapsid IgG or external confirmation), they will all be followed up until visit 5 (end of study).

9 Statistical Analysis

In this section the statistical analyses for the primary, secondary and exploratory endpoints are described. This section of the SAP is for Part B of the study, i.e. all statistical analyses described below will be performed using subject data from Part B only (not using subject data from Part A). There will be no blind review of the data before performing the statistical analyses. Individuals in Part A (followed-up as specified in protocol version V04_0) are analysed as outlined in Appendix A of this SAP.

9.1 Analysis populations

According to section 6.1.1 in the accompanying master protocol:

The primary dataset for analysis is derived from the intention-to-treat (ITT; Full Analysis Set, FAS) population. This dataset includes all trial subjects enrolled into the trial and randomised.

The evaluation is carried out strictly in accordance with the allocation by randomisation.

The secondary dataset for analysis is derived from the per-protocol (PP) population. This dataset includes all trial subjects who were treated according to protocol and reached a defined endpoint in the trial.

The tertiary dataset for analysis is the safety population. This population includes all trial subjects who received any IMP or other trial treatment.

Specific to this trial:

All analysis population defined here are specific for part B (using subjects from part B only).

Modified intention-to-treat population (mITT) Population.

The mITT population includes all subjects who received a study vaccine (as randomised and administered accordingly) and contributed both pre- and at least one post-vaccination blood sample for immunogenicity testing for which valid results were reported.

Primary Analysis Population

The primary analysis population is a subset of the modified intention-to-treat population (mITT), consisting of all randomised subjects whose primary endpoint measurement is

available. Please note the primary analysis population will include subjects with an anti-Nucleocapsid IgG at visit 2 indicative of SARS-CoV-2 infection.

Per Protocol Population

In the final analysis, protocol deviations will be reviewed to determine which protocol deviations may affect the analysis. The per protocol (PP) population includes all subjects in the mITT subset, but will exclude the following subjects:

- Data from all visits from subjects found to be ineligible at baseline
- Patients who have had a known new SARS infection between baseline and the visit concerned.
- Data from all visits subsequent to major protocol deviations that are considered to affect the outcome
- Data from any visits that occurred substantially out of the foreseen time window

Safety Population

The population for the safety analysis will be all randomised subjects that received a study vaccine. Analyses for the safety population will include safety reported through the end of the study.

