4.7.8. Blinding

No blinding is foreseen in this trial.

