Additionally, a sensitivity analysis will be performed on the per protocol analysis set, including only subjects who have been vaccinated and not having had a new infection between visit 1 and visit 2 using the anti-Nucleocapside IgG measurements of visit 1 and 2.

For subjects where the exact timepoint of an externally confirmed infection is available (i.e. subjects reports date of a SARS-CoV-infection confirmed outside study procedures, captured by AE reporting), a further sensitivity analysis will be performed excluding only those patients who had a an externally confirmed infection between randomisation and the observation of the primary endpoint.

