9.4 Secondary Endpoint Analyses

Summaries and analysis of the secondary endpoints will be based on the mITT population. If there are protocol deviations which may affect the analysis, a PP analysis may also be performed.

9.4.1 Secondary endpoints:

- Change in neutralizing antibody titre (Virus Neutralisation Assay) against wild-type 14 days after a 4th vaccination dose, to be determined in a subgroup only in which this type of assay has been performed.
- Change in neutralizing antibody titre (Virus Neutralisation Assay) **against variants of concern** 14 days after a 4th vaccination dose, to be determined in a subgroup only in which this type of assay has been performed.
- Antibody titre level **at 12 months** after a 4th vaccination dose measured by a quantitative enzyme-linked immunosorbent assay (anti-RBD-ELISA assay).
- Neutralizing antibody titre (Virus Neutralisation Assay) against wild-type SARS-CoV-2 at 12 months after a 4th vaccination dose, to be determined in a subgroup only in which this type of assay has been performed.
- Neutralizing antibody titre (Virus Neutralisation Assay) **against variants of concern** at 12 months after a 4th vaccination dose, to be determined in a subgroup only in which this type of assay has been performed.

For quantitative data the number of valid observations, mean, standard deviation, standard error, median, minimum and maximum will be calculated for each treatment group and each time point separately. Additionally, descriptive statistics of immunogenicity data may include Geometric Means (GM), Geometric Mean Fold Rise (GMFR) from baseline, and proportion of participants achieving a

pre-specified increase from baseline. Absolute values and the changes will be reported and visualized by individual trajectories of subjects over time via spaghetti plots. Furthermore, mean trajectories (such as means \pm sem) and boxplots will be provided.

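### Two judgement-based per-protocol exclusions can be decided with arm and titre visible, and the per-protocol check of GMT equivalence is optional

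*SAP*

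**What the plan says.** The SAP's section 9 opens its account of the Part B analyses with this: "There will be no blind review of the data before performing the statistical analyses". Section 9.1 then dates the deviation review: "In the final analysis, protocol deviations will be reviewed to determine which protocol deviations may affect the analysis". It lists four grounds for leaving the PP set:

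- ineligibility: "Data from all visits from subjects found to be ineligible at baseline";
- a known new infection between baseline and the visit concerned;
- visits after a major deviation that someone judges to bear on the outcome, with no list of such deviations;
- timing: "Data from any visits that occurred substantially out of the foreseen time window", with no number of days.

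The PP set is used in two main places. For the primary endpoint, SAP 9.3.2 commits to it: "a sensitivity analysis will be performed on the per protocol analysis set", with new infection identified from anti-N IgG at visits 1 and 2. For the secondary endpoints, SAP 9.4 does not commit: "If there are protocol deviations which may affect the analysis, a PP analysis may also be performed". SAP 9.4.3 adds PP analysis only as an example of how infection effects might be explored.

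On blinding, Protocol 4.7.8 is plain: "No blinding is foreseen in this trial". SAP section 3 nevertheless says: "This is a randomised controlled, adaptive, evaluator-blinded multicentre Phase II protocol evaluating immunogenicity and reactogenicity of different booster strategies". Neither document describes how an evaluator would be kept blind.

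**The concern.** A PP analysis tests whether a conclusion survives once deviating participants are removed. That test is worth something only if nobody can choose whom to remove after seeing what removal does. Here two of the criteria need a decision about each case, the review takes place within the analysis, and nothing requires arm or titre to be withheld.

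Equivalence is where this matters most. Deviations can make two arms look alike, so an mITT equivalence finding is normally read beside a PP one. Under SAP 9.4 that second analysis might not be run. If it is, its membership may have been settled with the anti-RBD results in view.

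**Working it through.** **Does any text fix PP membership before results are seen?**

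- SAP 9 excludes a blind review.
- SAP 9.1 places the review in the final analysis.
- Protocol 6.1.2 requires the SAP to be final before any analysis. That fixes the wording, not the classification of each deviation, and the wording itself defers classification.
- Protocol 6.1.1 gives only the master protocol's general PP definition and no trial-specific rules.
- SAP section 8 gives visit windows (day 14 ± 2 days; months 3, 6 and 12 ± 3 days) but not how far outside them a visit must fall to be excluded.

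Nothing fixes membership before titres by arm are visible.

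**When is the final analysis?** The term is undefined.

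- If it means the end-of-study analysis: the primary analysis is planned for October 2022, the last visit for September 2023 and database lock 30 days later. The PP set needed in SAP 9.3.2 would then be settled about a year after the primary analysis.
- If it means any analysis other than the interim one (SAP 9.10): the review falls in October 2022 and there is no gap. It is still made during the analysis and without blinding.

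**Plan's own figures.** For the primary rate, half-width = z × √(p(1−p)/n) with z = 2.2414 (97.5% two-sided), p = 0.5 and n = 250: 2.2414 × √(0.25/250) = 0.0709, which matches the stated ±7.1 points. For the margin, log10(0.67) = −0.1739, which matches ±0.174. Neither figure is in dispute.

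**Room for choice, as an upper bound.** Assumptions: 250 per arm, normal log10 titres, and SD 0.3 to 0.6 because the documents give no SD. Every excluded participant is taken from the lowest titres of one arm, and none from the other. Removing the lowest fraction f raises that arm's mean by SD × φ(z₁₋f)/(1−f). At f = 5% this is SD × 0.1031/0.95 = 0.109 SD. The 95% half-width for the difference is 1.96 × SD × √(2/250).

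| SD | Shift at 5% | Share of 0.174 | 95% half-width |
|---|---|---|---|
| 0.3 | 0.033 | 19% | 0.053 |
| 0.4 | 0.043 | 25% | 0.070 |
| 0.5 | 0.054 | 31% | 0.088 |
| 0.6 | 0.065 | 37% | 0.105 |

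Across the same SDs the shift is 0.015 to 0.030 at f = 2% and 0.058 to 0.117 at f = 10%.

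For the binary endpoint at 50%, removing 12 of 250 with the same outcome gives 125/238 = 52.5% or 113/238 = 47.5%.

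**The case against.** The case on the other side is substantial, and most of it limits the point without removing it.

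- **The main results do not depend on the PP set.** SAP 9.3 and 9.4 base the primary and secondary analyses, including equivalence, on mITT. A reader might infer that the primary rates or the equivalence test are themselves open to selection; the documents do not support that.
- **Infection is largely handled by rule.** SAP 9.3.2 commits to a model with infection as a factor, a PP analysis with an anti-N criterion, and an analysis excluding externally confirmed infections. SAP 9.4.3 extends the exploration to secondary endpoints. It would be wrong to conclude that the infection check fails.
- **The timing need not fail.** An interim analysis is planned, so *final* may only mean *not interim*. A year's delay is one reading and not an established fact.
- **The discretion is bounded.** All four categories are written in advance, two are largely rule-based, and a low titre is not a ground for exclusion. No passage says who reviews or what they see. The plan permits a review with results visible; it does not prescribe one.
- **The bound is extreme.** It needs the lowest titres in one arm all to carry excludable deviations. The documents give no deviation rate, and a move from 50% to 52.5% lies well inside ±7.1 points.

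One defence does not stand. Open-label treatment does not rule out a review without arm or titre. Deviations can be listed without either, and samples go to central laboratories (Protocol 4.9.3). The evaluator-blinded phrase in SAP section 3 gives no safeguard, because no mechanism is described.

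**Conclusion.** The point holds as a weakness in the PP robustness check, mainly for the day-14 GMT equivalence conclusion. Two undefined exclusion criteria can be applied with arm and anti-RBD titre visible, and the secondary PP analysis is optional on an undefined trigger. SAP 9.4 does not say when the choice to run that analysis is made; that it follows the deviation review is an inference.

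The size is a bound only: at most 19% to 37% of the margin for 5% one-sided exclusion, on assumed SDs of 0.3 to 0.6. It shows how much room the wording leaves, not what is likely to happen. No sample size, alpha level or main analysis changes. The correction is cheap and worth making.

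**What to change.** Replace the sentence in SAP 9 on blind review and the sentence in SAP 9.1 on the timing of the deviation review with text such as:

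> Before anti-RBD titres are merged with treatment group for the primary endpoint analysis, deviations are listed without treatment group or anti-RBD titre and classified against the list of major deviations in this SAP. PP membership for visits 1 and 2 is then fixed and dated. The same is done for visit 5 before final database lock. Out-of-window visits are defined by a stated number of days relative to the visit schedule. Infection exclusions are applied by algorithm (new anti-N positivity between visits, or an externally confirmed infection) and need no review of anti-RBD results.

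The SAP must then supply the list of major deviations and the day limit. If the interim analysis is held, membership for the participants in it should be fixed beforehand in the same way.

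In SAP 9.4, make the PP analysis of the day-14 GMT equivalence test a commitment instead of an option. Reconcile the evaluator-blinded wording in SAP section 3 (and Protocol 4.2) with the statement that there is no blinding.

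The cost is SAP wording and a short deviation review before each analysis. Anti-N and anti-RBD share a line in the visit schedule, so the data transfer must let anti-N be used without showing anti-RBD. A fixed day limit may also remove some late visits from the sensitivity set.
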